# 8.2.4. Proportion of participants achieving a sPGA score of 0 or 1 at Scheduled Timepoints (Estimand 6)

Proportion of participants with sPGA score of 0 or 1 with  $\geq 2$  grade improvement at scheduled timepoints up to Week 12 from Baseline will be plotted by treatment group.

# 8.2.4.1. Main Analysis Approach

Similar methods and intercurrent event strategies as applied in the main analysis provided for Estimand 5 analysis will be used to evaluate proportion of participants achieving a sPGA score of 0 (clear) or 1 (almost clear) with  $\geq$ 2 grade improvement from Baseline at scheduled timepoints up to Week 12 on FAS (see Section 8.2.3.1).

# 8.2.5. Change and percentage change from Baseline in PASI score at scheduled timepoints (Estimands 7a and 7b)

PASI observed scores will be tabulated by treatment group and visit; the corresponding changes from baseline and percentage change from baseline will be summarized.

#### 8.2.5.1. Estimand 7a

The endpoint is the percentage change from baseline in PASI score up until Week 12.

#### 8.2.5.1.1. Main Analysis Approach

A mixed model repeated measures (MMRM) of percentage change from baseline in PASI score up until Week 12, including terms for treatment, visit, baseline PASI score (as a continuous covariate), a treatment by visit interaction with an unstructured (UN) covariance matrix. The following additional covariates will be tested in the model using backward elimination with a significance level of 0.2 to retain the covariates in the model: age, BMI and weight as continuous covariates, sex, previous biologic therapy (Yes/No) (as per IRT) and geographic region (North America/Western Europe vs. Eastern Europe) (as per IRT) as discrete covariates. At the very least, previous biologic therapy and geographic region will be retained in the model. In case of nonconvergence of the MMRM with UN covariance structure, the first order heterogeneous autoregressive model [ARH(1)] will be fitted instead; if this model still fails to converge then the number of covariance parameters will be reduced further and the first order autoregressive model [AR(1)] will be fitted.

The difference in mean change and mean percentage change between treatments with 95% CI at each scheduled timepoint will be estimated. The data collected after use of a prohibited medication, or discontinuation of treatment for any reason will be set to missing (Hypothetical strategy). The FAS will be used for this analysis. The MMRM analysis will assume a missing-at-random (MAR) mechanism for missing data.

The least-square (LS) mean for change from baseline and percentage change from baseline in PASI score at each time point will be presented for each treatment group until Week 12. Contrasts will be used to compare DC-806 dose regimens versus Placebo at each scheduled visit with the two-sided p-value testing  $H_1$  against  $H_0$ .

For example, at Week 12:

#### Comparison 1

H0:  $\mu$  at Week 12 DC-806 800mg =  $\mu$  at Week 12 Placebo H1:  $\mu$  at Week 12 DC-806 800mg  $\neq \mu$  at Week 12 Placebo

#### Comparison 2

H0:  $\mu$  at Week 12 DC-806 600mg =  $\mu$  at Week 12 Placebo H1:  $\mu$  at Week 12 DC-806 600mg  $\neq \mu$  at Week 12 Placebo

#### **Comparison 3**

H0:  $\mu$  at Week 12 DC-806 400mg =  $\mu$  at Week 12 Placebo H1:  $\mu$  at Week 12 DC-806 400mg  $\neq$   $\mu$  at Week 12 Placebo

#### **Comparison 4**

H0:  $\mu$  at Week 12 DC-806 200mg =  $\mu$  at Week 12 Placebo H1:  $\mu$  at Week 12 DC-806 200mg  $\neq$   $\mu$  at Week 12 Placebo

where  $\mu_{DC-806 xx}$  and  $\mu_{placebo}$  denotes the true mean percentage change from baseline in PASI at each scheduled visit for each DC-806 dose regimens and placebo, respectively. (xx= 800mg, 600mg, 400mg, 200mg)

Percentage change from baseline in PASI will be plotted over time by treatment group.

#### 8.2.5.2. Estimand 7b

#### 8.2.5.2.1. Main Analysis Approach

The endpoint is the change from baseline in PASI score up until Week 12.

Similar methods and intercurrent event strategies as applied in the main analysis provided for Estimand 7a (see Sections 8.2.5.1.1).

# 8.2.6. Change and percentage change from Baseline in the percentage of BSA affected at scheduled timepoints (Estimand 8a/8b)

The endpoint is the percentage change from baseline in BSA score up until Week 12 (Estimand 8a) and change from baseline in BSA score up until Week 12 (Estimand 8b).

#### 8.2.6.1. Main Analysis Approach

Similar methods and intercurrent event strategies as applied in the main analysis provided for Estimand 7a/7b analysis will be used (see Sections 8.2.5.1.1 and 8.2.5.2.1).

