#### 8.1.1. Estimand 1a

#### 8.1.1.1. Main Analysis Approach

A participant receiving any prohibited medication or discontinuing the treatment due to related adverse event or requirement for prohibited medication prior to Week 12 visit will be considered as a non-responder (Composite strategy). If a participant discontinued treatment for reasons other than related adverse event or requirement for prohibited medication, PASI scores after the treatment discontinuation date will be set to missing (Hypothetical strategy). If a participant experienced any treatment interruption, PASI score reported after the treatment interruption will be used as reported (Treatment policy).

Participants without Week 12 PASI score (either due to hypothetical strategy implementation or missed visit) will be considered as non-responder.

A 2-sided, 2-sample Fisher's exact or Chi-squared test will be performed to assess a difference between active treatment groups (DC-806) versus Placebo in PASI-75 at Week 12 for the following comparisons on the FAS:

#### Comparison 1

H0: PASI-75 at Week 12  $_{DC-806\ 800mg}$  = PASI-75 at Week 12  $_{Placebo}$ H1: PASI-75 at Week 12  $_{DC-806\ 800mg} \neq$  PASI-75 at Week 12  $_{Placebo}$ 

#### Comparison 2

H0: PASI-75 at Week 12  $_{DC-806\ 600mg}$  = PASI-75 at Week 12  $_{Placebo}$ H1: PASI-75 at Week 12  $_{DC-806\ 600mg} \neq$  PASI-75 at Week 12  $_{Placebo}$ 

#### Comparison 3

H0: PASI-75 at Week 12  $_{DC-806 400mg}$  = PASI-75 at Week 12  $_{Placebo}$ 

H1: PASI-75 at Week 12  $_{DC-806 \ 400 mg} \neq$  PASI-75 at Week 12  $_{Placebo}$ 

#### Comparison 4

H0: PASI-75 at Week 12  $_{DC-806\ 200mg}$  = PASI-75 at Week 12  $_{Placebo}$ H1: PASI-75 at Week 12  $_{DC-806\ 200mg} \neq$  PASI-75 at Week 12  $_{Placebo}$ 

The number and percentage of participants who are defined as PASI-75 responder will be presented by treatment group. The p-value and unconditional odds ratio with its corresponding 95% CI will be presented in the active treatment group compared to the placebo group. All comparisons will be performed in a prespecified hierarchical procedure starting from the highest dose regimen to the lowest dose regimen.

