#### 8.1.2. Estimand 1b

#### 8.1.2.1. Main Analysis Approach

A participant receiving any prohibited medication or discontinuing the treatment due to related adverse event or requirement for prohibited medication prior to Week 12 visit will be considered as a non-responder (Composite strategy). If a participant discontinued treatment for reasons other than related adverse event or requirement for prohibited medication, PASI scores after the treatment discontinuation date will be set to missing (Hypothetical strategy). If a participant experienced any treatment interruption, PASI score reported after the treatment interruption will be used as reported (Treatment policy).

Participants without Week 12 PASI score (either due to hypothetical strategy implementation or missed visit) will be considered as non-responder.

The number and proportion of participants with PASI-75 with corresponding 95% CI will be presented by treatment group. The p-value, conditional odds ratio with its corresponding 95% CI, strata-adjusted difference in proportions between treatment groups (DC-608 – Placebo) with its corresponding 95% CI based on the large sample approximation method for binary data using

Mantel-Haenszel strata weights (Mantel, Haenszel 1959) and the Sato variance estimator (Sato 1989) will be presented in the active treatment groups compared to the placebo group.

In addition, a logistic regression model will be performed with PASI-75 at Week 12 as binary response and treatment and baseline PASI score (as a continuous covariate) as covariates on the FAS. The following additional covariates will be tested in the model using backward elimination with a significance level of 0.2 to retain the covariates in the model: age, BMI and weight as continuous covariates, sex, previous biologic therapy (Yes/No) (as per IRT) and geographic region (North America/Western Europe vs. Eastern Europe) (as per IRT) as discrete covariates. At the very least, previous biologic therapy and geographic region will be retained in the model. The conditional odds ratio, with Placebo as reference group, their corresponding 2-sided 95% CI and p-value will be presented.

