#### 8.2.2.1. Main Analysis Approach

Similar methods and intercurrent event strategies as applied in the main analysis provided for Estimand 1a/1b analysis will be used to evaluate proportion of participants achieving a sPGA score of 0 (clear) or 1 (almost clear) with  $\geq 2$  grade improvement from Baseline at Week 12 on FAS. (see Sections 8.1.1.1 and 8.1.2.1).

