#### 8.3.2. Quality of Life Assessments

Proportion of participants achieving BSA  $\leq 1\%$  psoriasis involvement at Week 12 will be analyzed similarly to Estimand 1a/1b (see Sections 8.1.1 and 8.1.2).

DLQI, Itch NRS and Skin Pain NRS observed scores will be tabulated by treatment group and visit; the corresponding changes from Baseline and percentage change from Baseline will be calculated and summarized.

DLQI, Itch NRS and Skin Pain NRS scores' mean ( $\pm$ SD) will be plotted over time by treatment group.

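### Read literally, the SAP adjusts change in BSA for baseline PASI rather than baseline BSA; naming baseline BSA is a minor but free gain in precision, mainly for absolute change (Estimand 8b)

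*SAP*

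**What the plan says.** The BSA change analysis is specified by cross-reference. SAP 8.2.6.1 states: "Similar methods and intercurrent event strategies as applied in the main analysis provided for Estimand 7a/7b analysis will be used". The Section 8 table is firmer. Its row for 8a/8b repeats the 7a/7b specification and changes only the response, to percentage and absolute change in BSA.

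The parent model, in SAP 8.2.5.1.1, is an MMRM "including terms for treatment, visit, baseline PASI score (as a continuous covariate), a treatment by visit interaction with an unstructured (UN) covariance matrix". The candidates for backward elimination are "age, BMI and weight as continuous covariates, sex, previous biologic therapy (Yes/No) (as per IRT) and geographic region". Baseline BSA is in neither list.

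For the exploratory endpoint of BSA at or below 1%, SAP 8.3.2 says only "psoriasis involvement at Week 12 will be analyzed similarly to Estimand 1a/1b". The model part of that parent is the logistic regression in SAP 8.1.2.1, with treatment and baseline PASI plus the same candidate list.

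BSA is assessed at Screening and Day 1 (Protocol 1.3; SAP 15.1), so a baseline value is available.

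**The concern.** For change in PASI the SAP adjusts for the endpoint's own baseline, which is usually the strongest predictor of a change score. The cross-reference loses that property for BSA: the literal model carries the baseline of a different scale. Absolute change in BSA depends on how much was affected at the start, and whatever baseline PASI does not explain stays in the residual.

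The BSA threshold analysis has a similar mismatch. Entry requires BSA of at least 10% with no upper limit (Protocol 5.1). Reaching 1% takes a 90% reduction from 10% (1 - 1/10), but 97.5% from 40% (1 - 1/40). Baseline BSA is therefore directly prognostic for this endpoint.

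At stake is precision on secondary and exploratory contrasts with about 45 participants per arm (SAP 4.2), and an open covariate choice that should be closed before unblinding.

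**Working it through.** The documents state no SD, correlation, effect size or power for BSA, so there is no plan figure to reproduce. Every SD, slope and correlation below is an assumption. Only the 45 per arm and the two-sided 5% level come from the SAP (4.2 and 4).

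**1. Week 12 alone, by slope.** Let b be the slope of absolute change on baseline BSA (sign ignored), S0 the baseline SD, Se the residual SD given baseline BSA, and r the correlation of baseline PASI with baseline BSA. Assume PASI adds nothing once BSA is known.

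Residual SD ratio (PASI model / BSA model) = sqrt(1 + b²·S0²·(1 - r²)/Se²)

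Assumed grid: b 0.3-0.7, S0 12-15, Se 8-10, r 0.5-0.8.
- Lowest (b 0.3, S0 12, Se 10, r 0.8): sqrt(1 + 0.09·144·0.36/100) = 1.02
- Highest (b 0.7, S0 15, Se 8, r 0.5): sqrt(1 + 0.49·225·0.75/64) = 1.51
- Central (b 0.5, r 0.65): 1.10 (S0 12, Se 10) to 1.23 (S0 15, Se 8)

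**2. Week 12 alone, by correlation.** Let k = SD at Week 12 / SD at baseline, and ρ = correlation of baseline with Week 12 BSA. In units of baseline variance:
- PASI model: k² + 1 - 2kρ - r²(1 - kρ)²
- BSA model: k²(1 - ρ²)

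Example, k = 1, ρ = 0.5, r = 0.7: (1 - 0.49·0.25)/0.75 = 0.8775/0.75 = 1.17, an SD ratio of 1.08. An effect with 80% power in the BSA model has 74% in the PASI model.

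Over ρ 0.3-0.7 and r 0.5-0.9:

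| k | SE increase | Power (80% with baseline BSA) |
|---|---|---|
| 1.0 | 2-18% | 66-79% |
| 0.7 | 9-43% | 50-73% |

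**3. Percent change, and a multiplicative response.** An ANCOVA simulation with 45 per arm, skewed baseline BSA and r 0.5-0.9 gave an SE for percent change (8a) 0-3% larger with baseline PASI. The increase is zero if percent response does not depend on baseline BSA. In the same simulation the SE for absolute change (8b) was 0.6-10% larger.

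**4. The SAP's model has one baseline slope for all visits.** There is no baseline-by-visit term. If the true slope is small at Day 8 and grows, the common slope is pulled towards the early, less variable visits. I took S0 = 13.5; residual SDs 3, 4, 6, 8, 9 at Days 8, 15, 29, 57, 85; and correlation 0.7 between adjacent visits, decaying as a power. The common slope g is the one that minimises the determinant of the residual covariance, as maximum likelihood does with an unstructured matrix. With baseline BSA the Week 12 variance is then S0²(b12 - g)² + Se².

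For the first row below: 13.5²·(0.5 - 0.064)² + 81 = 115.6, so the SD is 10.75.

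| True slopes over the five visits | g (BSA model) | Week 12 SD, BSA | Week 12 SD, PASI (r 0.8 to 0.5) | Ratio |
|---|---|---|---|---|
| 0.05, 0.10, 0.20, 0.35, 0.50 | 0.064 | 10.75 | 10.98-11.16 | 1.02-1.04 |
| 0.10, 0.20, 0.30, 0.40, 0.50 | 0.114 | 10.40 | 10.79-11.09 | 1.04-1.07 |
| 0.15, 0.20, 0.30, 0.40, 0.50 | 0.160 | 10.10 | 10.59-11.02 | 1.05-1.09 |
| 0.20, 0.25, 0.30, 0.40, 0.50 | 0.211 | 9.81 | 10.40-10.95 | 1.06-1.12 |
| 0.50 throughout | 0.500 | 9.00 | 9.87-10.73 | 1.10-1.19 |

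With a growing slope, swapping the covariate alone therefore gains roughly 3-11%. Letting the baseline BSA slope vary by visit would bring the Week 12 SD to 9.00 in every row. That further gain comes from the interaction, not from the choice of baseline.

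**The case against.** The best defence is that SAP 8.2.6.1 says similar, not identical. In the parent model baseline PASI is the endpoint's own baseline, so an analyst could fairly read the BSA version as using baseline BSA. That reading is open in the text, but two things weaken it. The Section 8 table says the same as 7a/7b with the response swapped. SAP 8.2.5.2.1 also uses the same cross-reference wording for 7b, where it means the same model with a new response. The defence shows that the intent may be right; it does not show that the plan settles the point.

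It also stands that baseline PASI already contains area affected (SAP 15.2), so it recovers part of the variance, and that the protocol calls its analyses descriptive and exploratory (Protocol 9.3). Sensitivity and supplementary subsections are not visible, so nothing is inferred from them.

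A reader might extend the point to sPGA, since SAP 8.2.2.1 says "Similar methods and intercurrent event strategies as applied in the main analysis provided for Estimand 1a/1b analysis will be used". The documents do not support a precision claim there:
- Entry requires sPGA of at least 3 (Protocol 5.1) on a 0-4 scale (SAP 15.3), so baseline sPGA is only 3 or 4.
- The test for 4a is unadjusted: "A 2-sided, 2-sample Fisher's exact or Chi-squared test will be performed". The Mantel-Haenszel difference for 4b names no baseline PASI. That covariate enters only the added logistic model and the GEE for Estimand 6.
- In a simulated logistic model with 45 per arm, the SE of the log odds ratio was 0.556-0.573 with baseline PASI, 0.553-0.572 with baseline sPGA and 0.566-0.582 with both. Power for the two single-covariate models differed by no more than about 1.5 points.

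**Conclusion.** The point holds for BSA. Read literally, change in BSA is adjusted for baseline PASI, and baseline BSA has no route into the model. The treatment comparison is not biased by this, because allocation is random.

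The loss falls mainly on absolute change (8b). In central cases the Week 12 residual SD is roughly 2-20% larger. It is nearer 3-11% larger under the SAP's single slope if the baseline effect grows over visits. For percent change (8a) the loss is about 0-3%. All of these rest on assumed SDs, slopes and correlations, and they shrink as the PASI-BSA correlation at baseline rises.

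For BSA at or below 1% no size was computed. The parent Fisher or chi-squared test is unadjusted, and adjustment in a logistic model does not in general shrink the SE of the odds ratio. The case there is that the prognostic baseline should be the one named.

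A reader might turn the upper central values into a large effective loss of sample: a ratio of 1.2 gives 1 - 1/1.2² = 31%. That is not supported as a headline. The ratio is assumed, applies only to absolute change, and ignores the common slope. At 1.03-1.11 the same sum gives 6-19%.

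This is a minor, free improvement on secondary and exploratory endpoints.

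**What to change.** - In SAP 8.2.6.1 and the 8a/8b row of the Section 8 table, name baseline BSA (continuous) as the baseline covariate in place of baseline PASI.
- Preferably add a baseline BSA-by-visit interaction, so that the Week 12 contrast gets the full benefit.
- In SAP 8.3.2, name baseline BSA as the baseline covariate in the logistic model for BSA at or below 1%.

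It would also help to state which baseline covariate is intended in the sPGA logistic and GEE models, for clarity only.

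The cost is SAP wording. No new data, visits or participants are needed, and the change should be made before unblinding.

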#### 8.3.2. Quality of Life Assessments

Proportion of participants achieving BSA  $\leq 1\%$  psoriasis involvement at Week 12 will be analyzed similarly to Estimand 1a/1b (see Sections 8.1.1 and 8.1.2).

DLQI, Itch NRS and Skin Pain NRS observed scores will be tabulated by treatment group and visit; the corresponding changes from Baseline and percentage change from Baseline will be calculated and summarized.

DLQI, Itch NRS and Skin Pain NRS scores' mean ( $\pm$ SD) will be plotted over time by treatment group.

#### 9. Safety Analysis

All safety analysis will be based on the safety analysis set (SAS). Participants will be summarized according to the treatment they actually received.

#### 9.1. Adverse Events

A TEAE is defined as an AE that occurs during or after the first study drug administration and up to and including the follow-up visit. For partially missing dates, the imputation rules described in Section 4.1 will be followed, and imputed dates will be used to determine whether an AE is treatment-emergent. If the start date is completely missing, then the AE is considered treatment-emergent if the end date (imputed or not) is on or after the date of first dose. If both the start and end dates are completely missing, then the AE is considered treatment-emergent.

All AEs will be coded using the latest MedDRA version available at the end of the study.

#### 9.1.1. Incidence Proportion of Adverse Events

Intercurrent event strategies described in Section 2.1 will be used.

An overall summary table for the SAS with count and percentage of participants with TEAEs and count of events will include:

- TEAEs
- TEAEs related to study drug
- TEAEs leading to treatment discontinuation
- TEAEs leading to treatment interruption
- Related TEAEs leading to treatment discontinuation
- TEAEs by greatest severity
- Serious TEAEs
- Serious TEAEs related to study drug
- TEAEs leading to death
- Deaths

A similar overall summary table will be provided for AESIs.

The incidence proportion of AEs will be summarized in tables with count and percentage of participants with AEs and count of events by SOC and preferred term (PT). Unless otherwise specified, at each level of SOC or PT, a participant with multiple events will only be counted once per SOC or PT. AEs will be displayed by treatment received for the SAS.

The following categories of AE will be summarized by SOC and PT:

- TEAEs
- TEAEs by greatest severity
- TEAEs by relationship
- TEAEs leading to treatment discontinuation
- TEAEs leading to treatment interruption
- Related TEAEs leading to treatment discontinuation
- Serious TEAEs
- Serious TEAEs by relationship

The following category of AE will be summarized by PT:

- TEAEs
- AESIs

At each level of SOC or PT, if a participant experiences more than one occurrence of the same AE, the occurrence with the greatest severity and the closest relationship with the study drug will be used in summary tables. All AEs will be presented in tables in descending order from the SOC with the highest total incidence proportion (across all treatment groups) to the SOC with the lowest total incidence proportion. Within each SOC, AEs will be sorted in descending order of PT based on the total of all treatment groups.

Listings of AE, AESI, Serious AE, and AEs that led to study drug discontinuation will be provided for the SAS.

# 9.1.2. Relationship of Adverse Events to Study Drug

The relationship or association of the study drug in causing or contributing to the AE will be characterized using the following classification and criteria:

- Not related: Evidence exists that the AE has an etiology other than the study drug (such as pre-existing condition, underlying disease, intercurrent illness, or concomitant medication)
- Unlikely related: a causal relationship between the study drug and the AE is not a reasonable possibility
- Possibly related: The event has a suggestive temporal relationship to the study drug, and an alternative etiology is equally or less likely
- Related: A temporal relationship exists between the event onset and administration of the study drug; it cannot be readily explained by the participant's clinical state or concomitant therapies and appears with some degree of certainty to be related based on the known therapeutic and pharmacologic actions of the drug; in case of cessation or reduction of the dose, the event abates or resolves and reappears upon rechallenge

For the purposes of summarizing AEs related to study drug, a relationship of 'Possibly Related' or 'Related' will be considered as related to study drug. A relationship of 'Not related' or 'Unlikely related' will be considered as not related to study drug. If an AEs relationship to study drug is missing, the relationship will be assumed to be 'Related'.

# 9.1.3. Severity of Adverse Event

The severity of AEs will be graded using the most current version of the National Cancer Institute Common Terminology Criteria for Adverse Events (CTCAE) Version 5.0 5-point scale:

- Grade 1 (Mild): Asymptomatic or mild symptoms; clinical or diagnostic observations only; intervention not indicated.
- Grade 2 (Moderate): Minimal, local, or noninvasive intervention indicated; limiting ageappropriate instrumental activities of daily living.
- Grade 3 (Severe): Medically significant but not immediately life-threatening; hospitalization or prolongation of hospitalization indicated; disabling; limiting self-care activities of daily living.
- Grade 4 (Severe): Life-threatening consequences; urgent intervention indicated.
- Grade 5 (Severe): Death related to AE

If an AEs severity is missing, the severity will be assumed to be Grade 3 (Severe). If a participant experiences more than one occurrence of the same AE, the occurrence with the greatest severity will be used in summary tables.

